7.1.1. Sensitivity Analysis

Sensitivity analyses include:

- Percent change from baseline in spot urinary UOx:Cr ratio by visits in Efficacy Analysis Set
- Percent change from baseline in spot urinary UOx:Cr ratio from Month 3 to Month 6 in Safety Analysis Set
- Percent change from baseline in ULNRatio (ratio of measured spot urinary UOx:Cr to ULN) from Month 3 to Month 6 in Efficacy Analysis Set

Percent change from baseline in spot urinary UOx:Cr ratio by visits in Efficacy Analysis Set will be analyzed using MMRM, LS means with corresponding SEM and 95% CIs will be displayed.

Percent change from baseline in spot urinary UOx:Cr ratio in Safety Analysis Sets will be analyzed using MMRM including all scheduled visits. LS mean with corresponding SEM and 95% CIs will be displayed.

To further adjust for any potentially confounding effect of natural maturation, the analysis of the ratio of spot urinary UOx:Cr ratio to the reference value (age-matched ULN established from the ULNs published in [Matos 1999]) that is established for healthy children of varying age will also be performed. Percent change from baseline in ULN Ratio from Month 3 to Month 6 in Efficacy Analysis Set will be analyzed using MMRM, and LS means with corresponding SEM and 95% CIs will be displayed. A sensitivity analysis will be conducted with the [REDACTED] (Bayesian) ULN (See SAP Addendum Version 1.0)

7.1.2. Analyses of 24-Hour Urinary Oxalate Excretion

24-hour urinary oxalate analysis will be conducted to assess the robustness of the primary outcome. Only valid 24-hour urinary oxalate values (see Section 6.2.1.1 of the protocol) will be considered for analysis for patients in Efficacy Analysis Set. The correlation between spot urine and 24-hour collection urine values maybe investigated. The analyses for 24-hour urinary oxalate corrected for BSA and 24-hour urinary UOx:Cr ratio will be carried out with data as observed. Percent change from baseline of 24h urinary oxalate corrected for BSA and 24h UOx:Cr ratio through Month 6 will be summarized.

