**Table 1: Schedule of Assessments –Primary Analysis Period (Screening through Month 6): All Patients**

*After Month 6, patients with weight <10 kg follow Table 2. Patients with weight ≥10 kg follow Table 4.*

Study Period Study Visit	Notes	Screening	6-Month Primary Analysis Period							
			Baseline	Wk 2	M1	M2	M3	M4	M5	M6
Study Day (±Visit Window)		-60 to -1	1 (±3)	15 (±14)	29 (±14)	57 (±14)	85 (±14)	113 (±14)	141 (±14)	169 (±14)
Study drug dosing in patients <10 kg	Dosing must be at least 21 days apart. Section 5.2.2; Table 7		X		X	X	X	X	X	X
Study drug dosing in patients ≥10 kg			X		X	X	X			X
Blood samples for PK analyses	See Table 5 for blood collection timepoints.		X							X
Blood samples for PD analyses	Collected predose, when applicable. Section 6.3.	X	X		X	X	X	X	X	X
24-hour urine collections for PD analyses	At Screening and Month 6, three collections are performed predose. For patients unable to comply, a single catheterized 24-hour collection may be performed. Section 6.2	X								X
Single-void urine collections for PD analysis (3 collections)	Following screening, 3 single-void collections are collected within 7 days predose (first morning voids are preferred). Section 6.2	X			X	X	X	X	X	X
Blood sample for pyridoxine (vitamin B6) levels	Only in patients receiving therapeutic pyridoxine. Do not collect within 6 hours of pyridoxine dose. Section 5.3	X	X				X			X
Renal stone events	Renal stone events are not considered AEs or SAEs. Section 6.3.3									
Renal ultrasound	Performed as per procedure manual. Section 6.3.4	X								X
Developmental assessment	Vineland Adaptive Behavior Scale. Section 6.7	X								X
Patient/caregiver experience and impact questionnaire	Section 6.8	X								X
ADA sample	Collect predose. Section 6.5.5.1		X		X		X			X

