5.4. Baseline Definitions

For spot urinary UOx:Cr ratio, baseline is defined as the mean of all spot urinary UOx:Cr ratio values collected prior to the first dose date/time of lumasiran. Baseline for all 24-hour urine parameters (i.e. 24-hour urinary oxalate corrected for BSA, etc) is defined as the median of all measurements collected prior to the first dose date/time of lumasiran. For all other PD parameters (i.e., plasma oxalate, etc.), baseline will use the mean of all measurements collected prior to the first dose date/time of lumasiran.

For other parameters, baseline is defined as the last non-missing value prior to the first dose date/time of lumasiran, unless otherwise specified. If multiple values are collected at a single visit (e.g. height, etc.), the mean of the values collected at the same visit will be used.

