7. STATISTICAL ANALYSIS

7.1. Primary Endpoint

The primary endpoint of this study is percent change in urinary oxalate excretion from baseline to the average of Month 3 to Month 6, which is measured by the primary outcome variable – percent change from baseline in spot urinary UOx:Cr ratio (mmol/mmol). The analysis will be conducted using the Efficacy Analysis Set.

Spot urinary UOx:Cr ratio is calculated from single-void urine collections. For all patients, triplicate single-void samples will be collected within 7 days prior to dosing, as specified in the Schedules of Assessment in the protocol. The mean value of these triplicate samples will be used as the baseline and postdose values in the analysis to account for the variability of the measure.

Despite historical data in healthy volunteers suggesting a natural decline in spot urinary UOx:Cr ratio in pediatrics, especially for children younger than 7 years old (Section 10.2.1), the effect of age on spot urinary UOx:Cr ratio in PH1 children is less clear (Section 10.2.2). Based on published data [Lieske 2005] at the time of writing of this SAP, it is considered that the potentially age-related decline in spot urinary UOx:Cr ratio level in children with PH1 is minimal, comparing with the anticipated treatment effect of lumasiran.

The primary analysis of the primary outcome variable will be performed using a restricted maximum likelihood (REML) based Mixed-effect Model Repeated Measures (MMRM) approach. Analysis will include fixed effects of scheduled visits and baseline spot urinary UOx:Cr ratio value (mmol/mmol), including patient as a random factor. An autoregressive (1) covariance structure will be used to model the within-patient error given the small sample size for this study. The primary estimate is the LS mean of the primary variable averaged over Month 3 to Month 6. This least square (LS) mean will be presented along with corresponding standard errors (SEMs), 95% confidence intervals (CI) and p-value from the model (i.e., testing against the null hypothesis of mean of primary outcome being equal to 0).

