8. CHANGES TO PLANNED ANALYSES

Summary of Changes from SAP V2.0	Rationale
Section 7.9 and Appendix 10.7 are added	To add the analysis plan for COVID-19 pandemic impact
Remove the imputation for analyses of 24-Hour Urinary Oxalate Excretion in Section 7.1.2	24-hour urine data are only available from few patients. Imputation planned initially will not lead meaningful results and thus will not be carried out
The definition of PK Analysis Set is changed in Section 4.1	PK Analysis Set is defined using all patients who received “one full” dose rather than “any amount” dose of lumasiran to account patients with adequate study drug exposure
Add additional analysis for changes in plasma oxalate for patients whose baseline POx \geq 1.5xLLOQ in Section 7.3	The LLOQ of the plasma oxalate assay is 5.55 μ mol/L. Due to the inability of quantify oxalate level below LLOQ by the assay, additional analysis is added so that meaningful reduction can be quantified
Change clinical laboratory data source and detailed analysis plan in Section 7.7.3	To align with the change in Protocol Amendment 2.0, the data handling for both central and local clinical laboratory data is added
Various editorial changes	To improve clarity

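### The 24-hour urine robustness check has no spot result in the same children, so agreement or disagreement may reflect who collected urine rather than how oxalate was measured

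*SAP*

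**What the plan says.** SAP 7.1.2 gives the purpose: "24-hour urinary oxalate analysis will be conducted to assess the robustness of the primary outcome". For the two 24-hour measures (BSA-corrected excretion and the 24-hour ratio), the analysis "will be carried out with data as observed". It is limited to valid collections, and percent change through Month 6 is summarised.

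Within the primary period these collections occur at two time points only. Protocol Table 1 notes "At Screening and Month 6, three collections are performed predose", with a single catheterized collection as the alternative. SAP Section 8 explains why imputation was dropped: "24-hour urine data are only available from few patients". No count is given.

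The result being checked is in SAP 7.1: "The primary estimate is the LS mean of the primary variable averaged over Month 3 to Month 6". It uses the spot ratio in the Efficacy Analysis Set.

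Three other provisions matter here:
- SAP 7.1.1: "Percent change from baseline in spot urinary UOx:Cr ratio by visits in Efficacy Analysis Set will be analyzed using MMRM". A Month 6 spot estimate will therefore exist, for the whole set.
- SAP 7.1.2: "The correlation between spot urine and 24-hour collection urine values maybe investigated". This is the only link between the two measures within children, and it is optional.
- SAP 5.4: for the spot ratio, "baseline is defined as the mean of all spot urinary UOx:Cr ratio values collected prior to the first dose date/time of lumasiran". The 24-hour measures use the median instead.

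**The concern.** The robustness question is about method: would the reduction look the same if oxalate were measured over 24 hours instead of in single voids? To answer it, the two figures should come from the same children at the same visit. As planned, the 24-hour summary comes from a self-selected few and the spot summaries from the whole efficacy set. Children able to collect for 24 hours, or allowed to be catheterized, may differ from the rest in age, weight band and baseline oxalate.

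If the 24-hour figure is read against the Month 3 to 6 mean, the visits differ as well. Under Protocol Table 1, children of 10 kg or more are dosed at Months 2, 3 and 6. Their predose urines at Months 3, 4, 5 and 6 therefore fall about 28, 28, 56 and 84 days after a dose.

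At stake is the meaning of the only primary-period check on the spot ratio in children under 6. The agreement data in SAP 10.3 come from patients aged 6 and over.

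**Working it through.** **1. The plan's own agreement figure.** SAP 10.3 gives a Pearson correlation of 0.86 (95% CI 0.82 to 0.90) from 156 pairs in 16 patients. A Fisher z interval with n = 156 gives 0.813 to 0.896 for r = 0.860, and 0.819 to 0.900 for r = 0.8649. The stated interval is reproduced within the rounding of r. It treats repeated pairs as independent; with n = 16 it would be 0.63 to 0.95. Either way, adding a constant to one measure leaves a correlation unchanged, so it cannot show a difference in mean reduction.

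**2. What a visit mismatch can do (SAP Table 2, Study 001B, percent reduction).**

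| Day | n | 24-hour | Spot | 24-hour minus spot |
|---|---|---|---|---|
| 85 | 13 | 63.2 | 60.9 | +2.3 |
| 113 | 13 | 70.8 | 60.0 | +10.8 |
| 141 | 13 | 70.9 | 63.9 | +7.0 |
| 169 | 11 | 63.3 | 70.2 | −6.9 |

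- Spot averaged over the four visits: (60.9 + 60.0 + 63.9 + 70.2)/4 = 63.75.
- 24-hour at Day 169 against that average: 63.3 − 63.75 = −0.45 points.
- 24-hour against spot at Day 169: −6.9 points.

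The Day 169 difference has a standard error of √(5.0² + 4.0²) = 6.4 if the two means are treated as independent. With r = 0.81 it is √(25 + 16 − 2 × 0.81 × 5 × 4) = 2.9. Each row carries one n for both measures, so the table illustrates the visit mismatch only and says nothing about a subset of children.

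**3. What pairing gains in precision.**

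Inputs:
- 24-hour variance 5.0² × 11 = 275 (SD 16.6).
- Spot variance 4.0² × 11 = 176 (SD 13.3, Day 169) or 6.0² × 13 = 468 (SD 21.6, Day 113).
- r = √0.656 = 0.81, from the percent-change regression in SAP 10.3.
- Assumption: k = 4 children with 24-hour data among N = 18, because the SAP gives no count.

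Formulas, with C = 2 × r × SD24 × SDspot (356 or 581):
- Unmatched: SE = √(SD24²/k + SDspot²/N − C/N).
- Paired: SE = √((SD24² + SDspot² − C)/k).

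Results:
- Spot SD 13.3: unmatched √(68.8 + 9.8 − 19.8) = 7.7; paired √((275 + 176 − 356)/4) = 4.9.
- Spot SD 21.6: unmatched √(68.8 + 26.0 − 32.3) = 7.9; paired √((275 + 468 − 581)/4) = 6.4.

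With N = 20 and k varied from 2 to 8, the unmatched SE runs from 11.3–11.5 down to 5.0–5.4, and the paired SE from 6.9–9.0 down to 3.4–4.5. The unmatched formula treats the k children as a random subset. Any selection adds bias that no standard error shows.

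**4. What remains imprecise.** At k = 4 the paired 95% half-width is 3.18 × 4.9 to 3.18 × 6.4, about 15 to 20 points. With N = 20 and a true difference of 10 points between methods, the two figures would still fall within 5 points of each other about 23% of the time unmatched and 15–21% paired. With no true difference, they would differ by more than 5 points about 52–53% of the time unmatched and 30–43% paired.

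**The case against.** The strongest reply is that SAP 7.1.2 names no comparator and no agreement criterion. The study is descriptive, the SAP is open about the sparse 24-hour data, and the Month 6 spot means in 7.1.1 can be placed beside the Month 6 24-hour summary. By-patient listings would let a reader pair the values by hand. On time, this stands: the plan can already close the visit mismatch. On children it does not, because no planned summary restricts the spot result to those with 24-hour data, and a listing is not a stated check.

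Four stronger readings are tempting and not supported:
- A reader might infer that the SAP formally compares the 24-hour figure with the Month 3 to 6 mean. That follows only from the stated purpose.
- A reader might take the 0.45 versus 6.9 contrast as proof that the methods disagree. The Day 169 difference is opposite in sign to the other three visits and rests on 11 older patients.
- A reader might call 7.1.2 the only 24-hour check in the trial. Protocol Table 9 schedules further collections at Month 12 and every 6 months after, and SAP 7.3 analyses them.
- A reader might say the spot ratio displaced the protocol's primary measure. Protocol 6.2 prefers 24-hour collection, but Protocol 7.2.5 itself names the spot ratio as the outcome variable.

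It is also fair to object that pairing does not rescue a sample of two to four children. That stands and limits the benefit.

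**Conclusion.** The point holds in a narrow form. The analysis described as a robustness check has no counterpart in the same children, so its result mixes measurement method with who collected urine, and also with visit if the Month 3 to 6 mean is used. The error can go either way: false agreement or false disagreement.

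The gain from pairing is modest: from about 7.7–7.9 to 4.9–6.4 points of standard error at an assumed 4 of 18 children. This rests on SDs and a correlation borrowed from older patients, with the correlation taken from repeated pairs pooled over visits. The main benefit is removing the confounding by subset. The differing baseline rules (mean for spot, median for 24-hour) would remain inside the paired difference. This is a minor improvement; the primary estimate is unaffected.

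**What to change.** Add to SAP 7.1.2: for children with valid baseline and Month 6 values on both measures, report n, each child's 24-hour and spot percent change at Month 6, and the mean within-child difference (24-hour minus spot) with a 95% CI. With fewer than 5 such children, show the individual values only. Use the same layout for both 24-hour measures and note the two baseline definitions beneath the table. State that this paired display is the robustness check and that it is supportive.

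The cost is one or two SAP sentences and one small table from data already collected. The downside is that the table may show less agreement than the unmatched summaries.

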7.2. Subgroup Analysis

Subgroup analyses will include analyses of the primary endpoint by age groups and weight-based dosing groups defined according to the baseline values:

Age group: 0-<1 year, 1-<6 years;

Weight-based dosing category: 0-<10 kg, \geq 10-<20 kg, and \geq 20 kg.

For primary analysis period, weight-based dosing category will be determined by initial dose level; for extension phase, dosing category may be analyzed both by initial dose level and by the dose level received for the longest duration.

Other subgroups may be examined, if deemed appropriate.

Subgroup analysis will be conducted for primary analysis of spot urinary UOx:Cr ratio in Efficacy Analysis Set to further understand the treatment effects. Descriptive statistics will be reported for the subgroups.

The subgroup analyses may be performed for secondary endpoints in Section 7.3.

7.3. Secondary Endpoints

For efficacy secondary endpoints, the Efficacy Analysis Set will be used; for PK secondary endpoints, the PK Analysis Set will be used.

Secondary endpoints in this study are as follows:

Extension Period (Month 6 to End of Study)

Percent change in spot urinary UOx:Cr ratio from baseline for all post-Month 6 visits will be summarized descriptively using the Efficacy Analysis Set. The analyses for 24-hour urinary oxalate corrected for BSA and 24-hour urinary UOx:Cr ratio will be carried out using Extension Period data as well.

Duration of Study (Baseline to End of Study)

Absolute changes in spot urinary UOx:Cr ratio and percent and absolute change in plasma oxalate from baseline using Efficacy Analysis Set will be performed similarly to primary analysis. In addition, percent and absolute change in plasma oxalate from baseline will also be analyzed using only patients in the Efficacy Analysis Set whose baseline plasma oxalate $\geq 1.5^*LLOQ$. LS means by postdose visits with corresponding SEM and 95% CIs will be displayed for the primary analysis period.

For continuous endpoints (including eGFR), descriptive statistics will be generated at each scheduled visit. Mean (+/- SEM) figures of actual values and changes from baseline will be plotted as well as individual spaghetti plots and listings. For binary endpoints, the number and associated percent of patients who met each threshold (e.g. $\leq ULN$ or $\leq 1.5 \times ULN$) at visits will be presented.

To demonstrate durability of the effect of lumasiran, for binary endpoints, (e.g. proportion of patients with spot urinary UOx:Cr ratio level $\leq ULN$ or $\leq 1.5 \times ULN$), tabular summaries of the number and percent of patients who met the threshold at post-baseline visits will be presented.

An analysis of the percentage of time that spot urinary UOx:Cr ratio is at or below the near-normalization threshold for the duration of study will be summarized. A patient is considered to have met the threshold if the spot urinary UOx:Cr ratio is $\leq 1.5 \times ULN$ at a post-baseline visit.

For each patient, the percentage of time that spot urinary UOx:Cr ratio is at or below the near-normalization threshold of $\leq 1.5 \times ULN$ will be calculated as follows:

$$\frac{\text{cumulative time at or below near normalization threshold}}{\text{cumulative time of valid assessments}} \times 100$$

where cumulative months in near-normalization will be defined as the summation across all intervals that met the near-normal threshold and cumulative months of valid assessments will be defined as the summation across all valid post-baseline collections.

Given that the sample collection varies during the study, the calculation of percentage of time will include the following considerations:

- Time will include all follow-up assessments until study end or premature treatment discontinuation, whichever occurs first.
- A linear interpolation method will be used to determine the bookend dates at which the patient crossed into the normal threshold and crossed out of the normal threshold

Descriptive statistics of percentage of time at or below the threshold (among the subset of patients who had at least one post-baseline value that met threshold) will be presented. In addition, the number of patients and associated percentage of patients in each category (e.g. <25%, ≥25% to <50%, ≥50% to <75%, ≥75% of time at or below the threshold) will also be presented.

Descriptive statistics of eGFR at and after 6 months of lumasiran will be presented using the Efficacy Analysis Set and Safety Analysis Set. Shift tables of eGFR categories from baseline to post-baseline visits and an overall worst post-baseline will also be generated

To demonstrate durability of the treatment effect of lumasiran, additional secondary endpoints may be assessed.

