### Duration of Treatment and Study

The duration of treatment with lumasiran is up to 60 months (a month is defined as 28 days). The

estimated total time on study for each patient is up to 62 months, including up to 2 months of screening followed by up to 60 months of treatment.

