10.2. Spot Urinary UOx:Cr Ratio Given Natural Growth

10.2.1. Natural decline of spot urinary UOx:Cr ratio in healthy pediatric population

Cross sectional studies, where the spot urinary UOx:Cr ratios were compared across broad age ranges (e.g., 1 - 6 months, 6 – 12 months, 1 – 2 years), showed that in young children over the age range of 0 to about 8 years, the urinary UOx:Cr ratio declines with increasing age. Data from healthy children ages 1 month to 17 years old (N=386) showed a decline in the 95th percentile of the spot urinary UOx:Cr ratio.[Matos 1999]. The decline in the UOx:Cr ratio appears to plateau after 7 years of age.[Matos 1999] A similar publication using data from 188 children from birth to 16 years old showed that the mean (and 5 – 95th percentiles) of the UOx:Cr ratio declined with increasing age, with no further decline observed in children ages 9 and above.[Leumann 1990]

[figure not shown]
On the other hand, longitudinal data based on 30 healthy infants where intensive random urine samples were collected starting from day 2 of birth with additional samples collected on weeks 2, 8, 16, 24 and 36 show that the mean UOx:Cr ratio stays stable over a period of 8 months (day 2 to week 36).[Morgenstern 1993] These findings are consistent with the results of another cross-sectional study where the mean (5 – 95th percentile) of UOx:Cr ratios stayed stable from birth up to 1 year of age.[Reusz 1995] Relative to other cross-sectional studies, Reusz compared UOx:Cr ratios using age categories with narrow age ranges.[Reusz 1995]

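### The only age-adjusted measure of effect size for spot UOx:Cr stops at Month 6, so a flat long-term percent reduction could hide some waning if untreated PH1 ratios fall with age

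*SAP*

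**What the plan says.** **Baseline.** SAP 5.4: "For spot urinary UOx:Cr ratio, baseline is defined as the mean of all spot urinary UOx:Cr ratio values collected prior to the first dose". It is not re-referenced as the child grows.

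**Extension.** SAP 7.3: "Percent change in spot urinary UOx:Cr ratio from baseline for all post-Month 6 visits will be summarized descriptively using the Efficacy Analysis Set". For the whole study, section 7.3 also plans "Absolute changes in spot urinary UOx:Cr ratio and percent and absolute change in plasma oxalate from baseline using Efficacy Analysis Set", handled like the primary analysis. The model for that analysis (SAP 7.1) has no age term: "Analysis will include fixed effects of scheduled visits and baseline spot urinary UOx:Cr ratio value (mmol/mmol), including patient as a random factor".

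**Maturation.** SAP 10.2.1 reports, from cross-sectional studies of healthy children, that "in young children over the age range of 0 to about 8 years, the urinary UOx:Cr ratio declines with increasing age". One study there reaches a plateau after 7 years of age, and another shows no further decline from age 9. The same section sets against this a longitudinal series in healthy infants that was stable to week 36, and a cross-sectional study that was stable to 1 year.

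**PH1.** SAP 7.1 calls the age effect in PH1 children less clear, then concludes that "the potentially age-related decline in spot urinary UOx:Cr ratio level in children with PH1 is minimal, comparing with the anticipated treatment effect". The support in SAP 10.2.2 is one value per patient from a registry: 15 children under 7 years, two of them under 2.

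**Adjustment.** SAP 7.1.1 gives natural maturation as the reason for one further analysis: "Percent change from baseline in ULNRatio (ratio of measured spot urinary UOx:Cr to ULN) from Month 3 to Month 6 in Efficacy Analysis Set". No counterpart is planned after Month 6.

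**The concern.** The adjustment is planned where drift has least time to act and is absent where it has most. Month 6 is 0.46 years after the first dose, and Month 60 is 4.60 years after it. The extension objective is the long-term effect on urinary oxalate. The natural reading of a flat percent-change curve is that the size of the effect has been maintained.

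Without a control arm, nothing in the trial shows what the untreated ratio would have done. If it falls as PH1 children grow, part of a late reduction from the pre-dose baseline is growth, and a steady curve is compatible with a weakening drug effect. The judgement that decline is minimal does not settle this. It is made for the primary endpoint and rests on single values per child, so it carries no information on change within a child over several years.

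**Working it through.** **1. Time scale.** Visit day = 1 + 28 × month. Month 60: 1 + 28 × 60 = 1681, which matches the protocol's schedule for the end-of-study visit. 1680 / 365.25 = 4.60 years. Month 6: 168 / 365.25 = 0.46 years, one tenth of that.

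**2. Time in the declining range.** Entry runs from term newborn to under 6 years (Protocol 4.1). Taking the plateau at 7 years: 7 − 4.60 = 2.40, so a child who enters at 2.4 years or younger stays below 7 throughout. Entry at 4 years gives 3.0 years below 7, and entry just under 6 gives about 1.0 year.

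**3. Raw reduction.** Let e be the true drug effect and f the untreated ratio as a fraction of its baseline value. Then

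raw reduction = 1 − (1 − e) × f, so e = 1 − (1 − raw) / f.

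The documents do not give f, so the values are assumed. For a reported 70%:

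- f = 1: e = 1 − 0.30/1 = 70%
- f = 0.75: e = 1 − 0.30/0.75 = 60%
- f = 0.5: e = 1 − 0.30/0.5 = 40%

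**4. Month 6 against Month 60.** As a reference effect, take 70.2%, the mean spot reduction at Day 169 in Study 001B (SAP 10.3, Table 2; patients aged 6 years and older). Assume a constant annual decline r over the whole period, so f = (1 − r)^years. The third and fourth columns hold the true effect constant at 70.2%. The last column is the true Month 60 effect if the reported curve stays flat at its Month 6 level.

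| Assumed r | Untreated fall by Month 60 | Reported at Month 6 | Reported at Month 60 | True Month 60 effect if curve is flat |
|---|---|---|---|---|
| 0% | 0% | 70.2% | 70.2% | 70.2% |
| 5% | 21.0% | 70.9% | 76.5% | 63.2% |
| 10% | 38.4% | 71.6% | 81.6% | 53.9% |
| 15% | 52.6% | 72.3% | 85.9% | 41.6% |

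For r = 10%: 0.90^4.60 = 0.616 and 0.90^0.46 = 0.953. Month 6 then reads 1 − 0.298 × 0.953 = 71.6%, and a flat curve implies 1 − 0.284/0.616 = 53.9% at Month 60. Over this range the shift at Month 6 is about 2 points or less. The table is for a child below the plateau throughout. Older entrants drift less.

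**5. What the ULN ratio does.** Let u be the ULN at the visit divided by the ULN at baseline. Then

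ULN-ratio reduction = 1 − (1 − raw) / u.

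With e = 70% and u = 0.75:

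- f = 1: raw = 70%; ULN-ratio = 1 − 0.30/0.75 = 60%. The raw figure is right.
- f = 0.75: raw = 1 − 0.30 × 0.75 = 77.5%; ULN-ratio = 1 − 0.225/0.75 = 70%. The ULN-ratio figure is right.

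The ULN-ratio figure is below the raw one whenever u < 1, whatever f is. If f = 1, a true 70.2% reads 1 − 0.298/0.8 = 62.8% when the ULN has fallen by 20%, and 1 − 0.298/0.6 = 50.3% when it has fallen by 40%.

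**The case against.** The strongest reply is that the SAP already has age-referenced long-term analyses. Section 7.3 links durability to the proportions at or below ULN and 1.5 × ULN, and section 3.2 defines these and the percentage-of-time endpoint by age. A falling ULN makes those thresholds harder to meet, so they do not share the possible bias. A reader might infer that long-term follow-up has no age reference at all. The documents do not support that.

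This limits the harm, but thresholds discard magnitude. As an assumed example, take a child at 10 × ULN with the ULN held constant. If the reduction wanes from 80% to 50%, the child moves from 2 to 5 × ULN and misses 1.5 × ULN throughout.

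Two other measures avoid spot creatinine. BSA-corrected 24-hour oxalate continues into the extension, but SAP section 8 says that few patients have 24-hour data. Change in plasma oxalate covers the whole study, but section 8 notes that the assay cannot quantify below 5.55 μmol/L. Both help, and neither gives the size of the effect on the spot ratio.

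The evidence for drift is also mixed. SAP 10.2.1 includes stable infant data, the PH1 effect is described as less clear, and many entrants may be old enough to reach the plateau early. This stands: the bias is possible, not demonstrated. But the stable data are from healthy infants and extend to 1 year at most.

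Finally, the extension summary is descriptive and no formal hypothesis is tested. Individual plots and listings are planned, and age subgroups of secondary endpoints are permitted but optional. This also stands. The issue is interpretation, not error rate.

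**Conclusion.** The gap is real and narrow. The SAP adjusts percent change for maturation over the first 0.46 years and not over the remaining follow-up to 4.60 years, and no other planned analysis supplies an age-adjusted size of effect on spot UOx:Cr. Over the assumed range f = 1 to 0.5, a reported 70% corresponds to a true effect between 70% and 40%. This rests on f, which the documents do not give, and on a multiplicative drug effect.

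Three stronger readings are not supported:

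- *Growth has been shown to inflate the long-term result.* The documents neither show nor exclude a fall with age in PH1.
- *The drug effect itself could be growth.* Drift alone would give a 70% reduction only if the untreated ratio fell by 70%. The question is whether the effect lasts.
- *Setting the raw and ULN-ratio results side by side would show whether PH1 ratios drift.* Step 5 shows that it cannot. One is a re-expression of the other through age, and the order of the two figures does not depend on f.

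The change is worth making as an inexpensive improvement. It does not affect the primary analysis.

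**What to change.** In SAP 7.3:

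1. For all post-Month 6 visits, report percent change from baseline in spot UOx:Cr divided by the ULN for age at that visit, beside the raw percent change and preferably by baseline age. Name the ULN source, normally the one used in section 7.1.1.
2. For the absolute-change endpoint, report absolute change in the ULN ratio. A percent change in the ULN ratio does not adjust an absolute change.
3. Present the raw and ULN-ratio results as a bracket. The raw figure is right if PH1 ratios do not fall with age, and the ULN-ratio figure is right if they fall in proportion to the ULN. State that the comparison cannot show which holds.
4. Base statements on the durability of effect size on both.

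In SAP 7.1, limit the judgement that age-related decline is minimal to the 6-month period.

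The cost is SAP wording and one further set of tables from data and ULNs already in the plan, with no new visits or samples. The downside is that, if PH1 ratios do not fall with age, the ULN ratio understates the long-term effect and can suggest waning that is not there. ULN age bands also add step changes as children cross them.
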